The proportion of subjects without pericarditis recurrence in the first 24 weeks of the RW period in each arm will be estimated using the KM method, as described in the analysis of the primary endpoint. The same censoring rules will apply. The variance of the difference in proportion between treatment arms will be the sum of the variance in each arm. The p-value and 95% CI will be calculated using a normal approximation.

8. Time to pericarditis pain NRS ≥ 4

Use the same method for the primary endpoint.

9. Time to CRP level ≥ 1 mg/dL. This is for elevation of CRP for which no other cause other than pericarditis was identified.

Use the same method for the primary endpoint. A manual review for any CRP ≥ 1 mg/dL will be performed to make sure that the CRP increase was caused by pericarditis.

10. Time to pericardial rub

Use the same method for the primary endpoint. Subjects with pericardial rub at RW baseline will be excluded from the analysis.

11. Time to widespread ST-segment elevation or PR-segment depression on ECG

Use the same method for the primary endpoint. Subjects with either condition at RW baseline will be excluded.

12. Time to new or worsening pericardial effusion on ECHO

Use the same method for the primary endpoint. Proportion of subjects with new or worsening in pericardial effusion on ECHO and its 95% CI in each arm will be estimated using the K-M method.

13. Change in category of ECHO pericardial effusion size at week 24 and end of RW based on central labs

- The ITT Week 24 analysis set will be used for this endpoint. Effusion size in ECHO has the following categories:
- None or Trivial/Physiologic
- Small
- Moderate
- Large
- Very Large
- NM/ND (Not Measurable/Not Recorded by Site)

Change in ECHO pericardial effusion size will be summarized by before and including bailout riloncept in each arm. Shift tables for change from RW baseline to RW weeks 24 and to end of RW visit will be generated. Due to potentially different number of subjects receiving bailout riloncept between treatment arms, there will be no hypothesis testing for this endpoint.

Endpoints 14-16 will be summarized for data before receiving bailout riloncept and for data including bailout riloncept in each arm. P-values will not be provided due to potentially different number of subjects receiving bailout riloncept.

14. Change over time in central-lab CRP level

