3.3. Testing Hypotheses and Multiplicity Adjustment

All statistical tests for the treatment comparison of efficacy endpoints in the RW period will be based on a 1-sided $\alpha=0.025$. For each endpoint, the null hypothesis is that the effects of riloncept and placebo are the same. The alternative hypothesis is that riloncept is better than the placebo.

In order to control the overall 1-sided type I error rate at the 0.025 level, a gatekeeping procedure in combination with Hochberg's procedure will be applied to testing the primary and major secondary endpoints. If the 1-sided p-value for testing the primary endpoint is ≤ 0.025 , a significant treatment effect on the primary endpoint will be claimed.

Section 5.2.2.1 provides the order of major secondary endpoints. If the primary endpoint is significant, the first major secondary endpoint, i.e., proportion of subjects who maintained clinical response at Week 16 of RW period will be tested at 1-sided $\alpha=0.025$. A significant treatment effect on this major secondary endpoint will be claimed if the 1-sided p-value is ≤ 0.025 . If the treatment effect is not significant on the primary endpoint, significance on this major secondary endpoint cannot be claimed regardless of the result.

If both primary and first major secondary endpoints are significant following the above procedure, the second and third major secondary endpoints defined in Section 5.2.2.1 will be tested with Hochberg's procedure at overall 1-sided $\alpha=0.025$. If both 1-sided unadjusted p-values are ≤ 0.025 , claim significance of riloncept for both endpoints. If the larger 1-sided p-value is > 0.025 , compare the smaller 1-sided p-value with 0.0125. If the smaller 1-sided p-value is ≤ 0.0125 , claim significance of riloncept on this endpoint.

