5.2.2.3. Other Secondary Efficacy Endpoints in the RW Period and Statistical Method

All time-to-event endpoints start from the day of randomization. The same censoring rules for the primary endpoint will be applied. Missing values will not be imputed unless otherwise specified. Analysis of secondary endpoints will be based on ITT analysis unless otherwise specified.

1. Proportion of subjects who maintained Clinical Response at Week 24 of the RW period based on ITT Week 24 analysis set

The same rules and method for the first major secondary endpoint will be applied, except that 16 weeks is replaced with 24 weeks.

2. Proportion of subjects who maintained Clinical Response at Week 8 of the RW period based on based on ITT Week 8 analysis set

The same rules and method for the first major secondary endpoint will be applied, except that 16 weeks is replaced with 8 weeks.

3. Percentage of days with minimal or no pain in the first 24 weeks post randomization based on ITT Week 24 analysis set

The same rules and method for the second major secondary endpoint will be applied, except that 16 weeks is replaced with 24 weeks.

4. Percentage of days with minimal or no pain in the first 8 weeks post randomization based on ITT Week 8 analysis set

The same rules and method for the second major secondary endpoint will be applied, except that 16 weeks is replaced with 8 weeks.

5. Proportion of subjects with absent or minimal pericarditis symptoms (based on the 7-point PGIPS) at Week 24 of the RW period based on subjects who were randomized at least 24 weeks before data cutoff

The same rules and method for the third major secondary endpoint will be applied, except that 16 weeks is replaced with 24 weeks.

6. Proportion of subjects with absent or minimal pericarditis symptoms (based on the 7-point PGIPS) at Week 8 of the RW period based on subjects who were randomized at least 8 weeks before data cutoff

The same rules and method for the third major secondary endpoint will be applied, except that 16 weeks is replaced with 8 weeks.

7. Proportion of subjects without pericarditis recurrence in the first 24 weeks of the RW period

The proportion of subjects without pericarditis recurrence in the first 24 weeks of the RW period in each arm will be estimated using the KM method, as described in the

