analysis of the primary endpoint. The same censoring rules will apply. The variance of the difference in proportion between treatment arms will be the sum of the variance in each arm. The p-value and 95% CI will be calculated using a normal approximation.

8. Time to pericarditis pain NRS ≥ 4

Use the same method for the primary endpoint.

9. Time to CRP level ≥ 1 mg/dL. This is for elevation of CRP for causes.

Use the same method for the primary endpoint. A manual review for any CRP ≥ 1 mg/dL will be performed to make sure that the CRP increase was caused by pericarditis.

10. Time to pericardial rub

Use the same method for the primary endpoint. Subjects with pericardial rub at RW baseline will be excluded from the analysis.

11. Time to widespread ST-segment elevation or PR-segment depression on ECG

Use the same method for the primary endpoint. Subjects with either condition at RW baseline will be excluded.

12. Time to new or worsening pericardial effusion on ECHO

Use the same method for the primary endpoint. Proportion of subjects with new or worsening in pericardial effusion on ECHO and its 95% CI in each arm will be estimated using the K-M method.

13. Change in category of ECHO pericardial effusion size at week 24 and end of RW based on central labs

- The ITT Week 24 analysis set will be used for this endpoint. Effusion size in ECHO has the following categories:
- None or Trivial/Physiologic
- Small
- Moderate
- Large
- Very Large
- NM/ND (Not Measurable/Not Recorded by Site)

Shift tables for change from RW baseline to RW weeks 24 and to end of RW visit will be generated. Due to potentially different number of subjects receiving bailout rilonacept between treatment arms, there will be no hypothesis testing for this endpoint.

Endpoints 14-16 will be summarized for data before receiving bailout rilonacept and

for data including bailout riloncept in each arm. P-values will not be provided due to potentially different number of subjects receiving bailout riloncept.

14. Change over time in central-lab CRP level

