Section 3.4: Subgroups to be Analyze Type of pericarditis: idiopathic, post pericardiotomy syndrome, Dressler's syndrome, and Still's disease	Deleted	Categories are almost identical to categories for diagnosis of recurrent idiopathic pericarditis (RI baseline): yes or no
Section 4: included Run-in Week 12 Analysis Set	Removed Run-in Week 12 Analysis Set	All subjects enrolled 12 weeks before the cutoff.
Section 5.1.3 and 5.1.5: Baseline and concomitant pericarditis medication categories: – Non-opioid analgesics – Opioid analgesics – Aspirin – NSAIDs – Colchicine – Oral corticosteroids – IM/IV corticosteroids – Other	Baseline and concomitant pericarditis medication categories: – Analgesics – Non-opioid analgesics – Opioid analgesics – NSAIDs – Aspirin – Other NSAIDs – Colchicine – Corticosteroids – Oral corticosteroids – IM/IV corticosteroids – Other	To reorganize categories
Throughout the SAP: rescue medications (ORT or prednisone)	rescue medications (ORT or corticosteroid)	To change the wording from “prednisone” to “corticosteroid” to include all types of corticosteroid
Section 5.2.1.1: Table 1 has no footnote	Added footnote below to Table 1 “*Excluding subjects receiving ORT/corticosteroid while waiting for at least 5 days since previous administration of study medication before receiving bailout riloncept or within 5 days prior to recurrence visit.”	To clarify the definition of using ORT/Corticosteroid.

Analysis in the draft SAP submitted to FDA on 03APR2020	Analysis in the final signed off version 1.0	Reason
Section 5.2.2.3 endpoint #9 time to CRP	Removed condition of CRP increase caused of pericarditis recurrence from the definition.	CRP increase is not specific to pericarditis recurrence. However, it is challenging to determine whether a CRP increase is caused by pericarditis recurrence or not. So, we decided to remove this condition.
Section 5.2.2.3 endpoint #13: Change in ECHO pericardial effusion size will be summarized by before and including bailout riloncept in each arm.	Deleted	Central ECHO data collected change from previous visit which is not change from baseline. Shift tables for effusion size were produced to summarize the change from baseline.
Section 5.2.2.3 endpoint #16: The CMH test stratified by the randomization strata will be applied.	Deleted	SAP specified that for Endpoints 14-16, p-values will not be provided. This sentence was left in the SAP inadvertently.

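### SAP v2.0 endpoint 9 (time to CRP ≥1 mg/dL) has lost its pericarditis restriction but keeps the manual cause review that served it, so it is unclear which CRP rises count as events

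*SAP*

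**What the plan says.** Endpoint 9 in SAP v2.0, Section 5.2.2.3, has three parts.

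- **Definition.** After naming the CRP threshold of 1 mg/dL, the text reads "This is for elevation of CRP for causes". No restriction on cause can be read from this.
- **Method.** "Use the same method for the primary endpoint". Under Section 5.2.1.2 that means a stratified log-rank test, Kaplan-Meier estimates and a stratified Cox hazard ratio. The opening of Section 5.2.2.3 adds: "The same censoring rules for the primary endpoint will be applied".
- **Event check.** Every CRP value at or above the threshold gets a manual review, "performed to make sure that the CRP increase was caused by pericarditis".

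The same file holds SAP v1.0 and a summary of the changes from v1.0 to v2.0, dated 16 June 2020. In v1.0 the definition read "This is for elevation of CRP for which no other cause other than pericarditis was identified", and the review sentence was the same as now. The summary describes the v2.0 change to endpoint 9 as "Removed condition of CRP increase caused of pericarditis recurrence from the definition". Its reason is that a CRP increase is not specific to pericarditis recurrence and that "it is challenging to determine whether a CRP increase is caused by pericarditis recurrence or not".

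**The concern.** In v1.0 the definition and the review belonged together: the definition limited events to rises without another cause, and the review enforced the limit. In v2.0 the limit is gone and the enforcement remains. A programmer working from v2.0 cannot tell whether a CRP of 1 mg/dL or more during, say, an unrelated infection is an event.

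A laboratory threshold is normally an objective event. If the review sentence is applied, each crossing has to pass a judgement on cause, and the SAP gives no criteria for it. The event status of each subject feeds directly into the log-rank test and the hazard ratio. At stake are the estimate and p-value of this one secondary endpoint, and whether another analyst could reproduce its event list.

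**Working it through.** The SAP gives no figure for this endpoint, so there is nothing to reproduce. The check is a comparison of texts, followed by an illustration of size.

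**1. Definition against review**

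| Source | Cause restriction in definition | Manual cause review |
|---|---|---|
| SAP v1.0, endpoint 9 | Yes | Yes |
| SAP v2.0, endpoint 9 | None readable | Yes, unchanged |
| Summary of changes, endpoint 9 | Stated as removed | Not mentioned |

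The mismatch lies within the v2.0 text itself. The summary of changes only shows that removing the restriction was intended.

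**2. Which event sets v2.0 allows**

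- (a) The first CRP ≥1 mg/dL from any cause, which follows from the definition and the stated intent.
- (b) The first CRP ≥1 mg/dL that the review attributes to pericarditis, which follows from the review sentence.

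The two differ by every rise judged to have another cause. The documents do not say how many of these there are.

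**3. What happens to a rise attributed to another cause**

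It could be ignored with the subject still at risk, treated as a censoring time, or kept as an event. Endpoint 9 takes over the primary censoring rules, but Table 1 in Section 5.2.1.1 deals only with pericarditis recurrence and does not cover this case.

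**4. Whether a test result is produced**

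Section 3.3 sets a 1-sided level of 0.025 for "All statistical tests for the treatment comparison of efficacy endpoints in the RW period". Section 5.2.2.3 expressly drops testing or p-values for endpoints 13, 14–16, 18–23, 25 and 26. Endpoint 9 is not on that list, so a log-rank p-value is to be expected. Endpoint 9 is also not part of the gatekeeping and Hochberg sequence, which covers the primary and the three major secondary endpoints.

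**5. Illustration of size**

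Inputs from SAP Section 2.3.1: placebo median 8 weeks and hazard ratio 0.244, both planned for adjudicated recurrence. Borrowing them for pericarditis-related CRP rises is an assumption. A constant rate *b* of unrelated rises, equal in both arms, is a further assumption with no source in the documents.

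- Placebo hazard: h = ln 2 / 8 = 0.0866 per week.
- Any-cause hazard ratio: (0.244 × h + b) / (h + b).
- Share of subjects with an unrelated rise by Week 16: 1 − exp(−16b).

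| b per week | Calculation | Any-cause HR | Unrelated rise by Week 16 |
|---|---|---|---|
| 0.005 | (0.0211 + 0.005) / (0.0866 + 0.005) | 0.285 | 7.7% |
| 0.01 | (0.0211 + 0.01) / (0.0866 + 0.01) | 0.322 | 14.8% |
| 0.02 | (0.0211 + 0.02) / (0.0866 + 0.02) | 0.386 | 27.4% |

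The comparator is 0.244, which would be seen if attribution were perfect. The table shows the dilution from counting all causes. It does not measure the effect of discretion in the review.

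**The case against.** The strongest reply is that this is an incomplete edit whose intended outcome is already on record. The review sentence is carried over from v1.0, the summary of changes says the condition was removed, and the same summary admits that another sentence, under endpoint 16, had stayed in the plan inadvertently. That stands, and it argues for calling the sentence an apparent leftover. It does not remove the need to correct it: the summary does not mention the review sentence, and an analyst who follows v2.0 to the letter would still apply it.

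The missing criteria could be in a separate review plan, and v2.0 does not say that the review is unblinded. That also stands. The SAP does, however, state such safeguards elsewhere: blinded verification of analysis sets (Section 4.7), per-protocol criteria fixed before unblinding (Section 4.5), blinded deviation review (Section 5.1.7), and written criteria for the Clinical Endpoint Committee (Section 5.2.1.2). Nothing assigns the CRP review to that committee.

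The garbled phrase in the definition may have lost a word in the source or when the PDF was read. The point therefore rests mainly on the review sentence.

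The illustration is open to fair criticism. It uses hazards for a different event, its rates are unsourced, and it treats rises as observed continuously. Table 5 schedules central CRP every 4 weeks to Week 24, so short rises between visits could be missed and the dilution may be smaller than shown.

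**Conclusion.** The point holds as an internal inconsistency in v2.0. The definition carries no readable cause restriction, yet the review sentence still calls for one, without criteria and without a rule for rises attributed elsewhere. Taken literally, the plan makes the event set of a log-rank and Cox endpoint depend on a judgement that the sponsor had decided to drop.

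A reader might infer two stronger things, and the documents support neither. One is that the sponsor found attribution unworkable or unreliable; it says only that it is challenging. The other is that the sponsor chose a subjective filter for this endpoint; the record points to a sentence left behind.

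The effect on the hazard ratio and p-value cannot be derived from the documents, and the range of 0.29 to 0.39 depends wholly on the assumptions stated with it. Priority is minor. Endpoint 9 is one of the other secondary endpoints, so type I error control and the primary and major secondary conclusions are untouched.

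**What to change.** In Section 5.2.2.3, endpoint 9:

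1. Delete the manual-review sentence.
2. Replace the garbled definition with one saying that the event is the first CRP ≥1 mg/dL after randomization, regardless of cause.
3. If a version limited to pericarditis-related rises is wanted, label it a sensitivity analysis. Give it written criteria applied blind to treatment, and state whether a rise attributed to another cause is ignored, censored or counted.

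This costs an edit of two sentences and carries out a change that the sponsor has already recorded. The price is some dilution of the hazard ratio toward 1 from unrelated CRP rises, of a size the documents do not allow one to state.

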5.2.2.1. Definition of Major Secondary Efficacy Endpoints in the RW Period

This section defines 3 major secondary endpoints. These endpoints will be analyzed with the ITT Week 16 analysis set. Handling of missing data due to end of RW period will be discussed in Section 5.2.2.2.

1. Proportion of subjects who maintained clinical response at Week 16 of the RW period. clinical response is defined as a weekly average of daily pericarditis pain on the 11-point NRS ≤ 2.0 and CRP level ≤ 0.5 mg/dL, and on monotherapy of randomized study drug at Week 16.

Subjects who complete 16-week of double-blinded treatment and meet the clinical response criteria at Week 16 will be considered as responders. Subjects who had recurrence, discontinued double-blinded treatment, lost to follow-up, and used bailout riloncept or rescue medications (ORT or corticosteroid) before Week 16 will be considered as non-responders.

If either weekly average of NRS or CRP is missing at week-16 assessment, the subject will be considered as a non-responder.

2. Percentage of days with pain NRS ≤ 2 in the first 16 weeks of the RW period. No or minimal pain is defined as non-missing NRS ≤ 2 .

The denominator will be 112 (=16x7) for every subject. NRS assessments after treatment termination will be included. NRS assessments while on rescue medications for pericarditis will considered not meeting this criterion. Receiving each administration of bailout riloncept will disqualify for meeting NRS ≤ 2 for 7 days. Missing values will be counted as 0 day meeting the criterion.

3. Proportion of subjects with absent or minimal pericarditis symptoms (based on the 7-point PGIPS) at Week 16 of the RW period.

Subjects who do not have the assessment due to early termination or other reasons will be considered as not meeting the criterion. Subjects who took rescue medications at the Week 16 assessment or used bailout riloncept on or before Week 16 will also be considered not meeting the criteria.

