A mixed model with repeated measures (MMRM) using TYPE=UN option in SAS Proc Mixed will be applied in the analysis of this endpoint. If the model does not converge, an analysis of covariance (ANCOVA) model will be used at each timepoint to calculate least-squares (LS) means. In the model, subjects will have repeated measures for the response variable change from baseline of the endpoint. The explanatory variables will include the baseline value, treatment arm, baseline value by treatment interaction, and the variables for randomization strata. Only observed values will be used in the analysis without imputation.

15. Change over time in the subject's assessments of pericarditis pain (weekly averages)

The same method for change over time in CRP level will be applied. If bailout riloncept is used in a week, the week will be considered as after bailout.

16. Number (percentage) of subjects with absent or minimal pericarditis activity over time after RW week 24 based on the PGIPS. The denominator in each arm will be the total number of subjects with the assessment at each visit.

17. Number (percentage) of subjects with absent or minimal pericarditis activity over time based on the PGA-PA. The denominator in each arm will be the total number of subjects with the assessment at each visit.

The same analysis method and analysis sets for PGPIS will be applied.

The endpoints below (18 – 23) from patient reported outcomes will be summarized with descriptive statistics. There will be no hypothesis testing since they are measured at RW baseline and Week 24 only and receiving bailout riloncept due to recurrence at Week 24 could be a confounding factor.

18. Change from baseline to week 24 in the SF-36 Physical and Mental Component Scores (see below for definition)

19. Change from baseline to week 24 in Physical Functioning, Role-Physical, Bodily Pain, General Health, Vitality, Social Functioning, Role-Emotional, and Mental Health domains in SF-36.

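### Endpoint 17 (PGA-PA over time in the RW period) pairs an observed-case denominator with a cross-reference to PGIPS rules that do not fit it at Weeks 8, 16 and 24, and states no rule for ratings made on bailout rilonacept

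*SAP*

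**What the plan says.** All references are to SAP version 2.0 (16 June 2020).

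- **Endpoint 17, Section 5.2.2.3.** The endpoint is "Number (percentage) of subjects with absent or minimal pericarditis activity over time based on the PGA-PA", with no limit on weeks. Two instructions follow. The first sets the denominator: "The denominator in each arm will be the total number of subjects with the assessment at each visit". The second is a cross-reference: "The same analysis method and analysis sets for PGPIS will be applied". The acronym is evidently a misspelling of PGIPS.
- **PGIPS at Weeks 8, 16 and 24.** Major secondary endpoint 3 (Section 5.2.2.1) is analysed in the ITT Week 16 set. On missing data: "Subjects who do not have the assessment due to early termination or other reasons will be considered as not meeting the criterion". Rescue medication at the Week 16 assessment is also a failure, and so is bailout: subjects who "used bailout riloncept on or before Week 16 will also be considered not meeting the criteria". Section 5.2.2.2 gives a stratified CMH test. Endpoint 5 carries this to Week 24: "The same rules and method for the third major secondary endpoint will be applied, except that 16 weeks is replaced with 24 weeks". Endpoint 6 does the same for Week 8.
- **PGIPS after Week 24.** Endpoint 16 uses the same denominator sentence as endpoint 17, and names neither an analysis set nor a test.
- **Bailout paragraph.** "Endpoints 14-16 will be summarized for data before receiving bailout" and again including bailout, and no p-values are given. Endpoint 17 is not named there. It is not named either in the later paragraph that rules out testing for endpoints 18 to 23.
- **Schedule.** Table 5 has PGIPS and PGA-PA at the same RW visits, including Weeks 8, 16 and 24.

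**The concern.** A programmer given endpoint 17 cannot tell how to score a subject who recurred, moved to open-label bailout rilonacept and was then rated by the physician. The denominator sentence keeps that subject in. The PGIPS rules at the same visit make the subject a failure.

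Bailout is given in both arms, irrespective of assignment, but the plan expects far more recurrences on placebo. Under the observed-case rule, a placebo subject rated absent or minimal while on bailout rilonacept is a success for placebo. The comparison then mixes the effect of the randomized treatment with the effect of rescue by the study drug. The plan recognises this problem nearby: it gives it as the reason for no testing of endpoint 13, no p-values for 14-16 and no testing of 18-23. Endpoint 17 falls between these ranges with no rule.

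At stake is the reading of two parallel global ratings. If the arms differ clearly on PGIPS and only slightly on PGA-PA, the cause could be the scoring rule rather than any disagreement between patient and physician.

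**Working it through.** **1. Can the two instructions both apply?**

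| | PGIPS, Weeks 8/16/24 | PGIPS after Week 24 (endpoint 16) | PGA-PA, all visits (endpoint 17) |
|---|---|---|---|
| Denominator | ITT Week-N set | subjects assessed | subjects assessed |
| Missing assessment | failure | excluded | excluded by the denominator sentence |
| Bailout by the visit | failure | shown before / including bailout | not stated |
| Test | stratified CMH | no p-values | not stated |

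A subject without an assessment cannot be both excluded from the denominator and counted as a failure. So if the cross-reference reaches the first column, the two sentences of endpoint 17 conflict at Weeks 8, 16 and 24. If it reaches only the second column they agree, but PGA-PA at those three visits is then scored differently from PGIPS.

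**2. Design inputs (Section 2.3.1).** Exponential times, placebo median 8 weeks, hazard ratio 0.244, one-sided 2.5%, power 90%, about 25 per arm. The plan's own figure reproduces: the Schoenfeld formula gives 22 events, with power 0.911 at 22. The plan states no figure for endpoint 17.

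**3. Recurrence-free share.** Placebo S_P(t) = 0.5^(t/8); rilonacept S_R(t) = S_P(t)^0.244.

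| Week | Placebo | Rilonacept | Difference | Expected recurrences of 25 (placebo, rilonacept) |
|---|---|---|---|---|
| 8 | 50.0% | 84.4% | 34.4 points | 12.5, 3.9 |
| 16 | 25.0% | 71.3% | 46.3 points | 18.8, 7.2 |
| 24 | 12.5% | 60.2% | 47.7 points | 21.9, 9.9 |

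**4. Response rate under each rule.** Let b be the share of recurrences that receive bailout and r the share of bailed-out subjects rated absent or minimal. Neither is in the SAP. Assume also that all recurrence-free subjects respond, that recurrences without bailout do not, and that no assessments are missing.

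- Bailout as failure: rate = S, so the gap is S_R − S_P.
- Observed denominator: rate = S + (1 − S)·b·r, so the gap is (S_R − S_P)·(1 − b·r).

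Week 16 under the observed denominator, with b = 1, where the gap is 46.3 × (1 − r):

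| r | Placebo | Rilonacept | Gap |
|---|---|---|---|
| 0 | 25.0% | 71.3% | 46.3 points |
| 0.5 | 62.5% | 85.7% | 23.2 points |
| 0.8 | 85.0% | 94.3% | 9.3 points |
| 1.0 | 100% | 100% | 0 |

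With b = 0.75 the Week 16 gap is 28.9 points at r = 0.5, 18.5 at r = 0.8 and 11.6 at r = 1. At Week 24 with b = 1 it is 23.9, 9.5 and 0 points at the same three values of r.

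**The case against.** The best defence is that the cross-reference means endpoint 16, directly above. Both endpoints use the same denominator sentence and both speak of activity, whereas major secondary 3 and endpoints 5-6 speak of symptoms. Endpoints 1-6 carry over rules and method, while endpoint 17 carries over method and sets and does not mention rules. Section 3.1 makes observed data the default for by-visit analyses. On this reading endpoint 17 is internally consistent, and the split by bailout might be inherited as part of the method.

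That reading is plausible, so a flat contradiction is not proven. It does not close the point. Endpoint 16 starts only after Week 24 and endpoint 17 does not. The reference is to analysis sets in the plural, and endpoint 16 names none. Its CMH sentence was removed in version 2.0 because endpoints 14-16 carry no p-values, so it now states no test to inherit. The observed-data default says nothing about bailout.

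Two stronger inferences are tempting and unsupported:

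- A reader might infer that rescued placebo subjects are scored as successes outright. They count only if rated absent or minimal, and the same holds for bailed-out subjects in the rilonacept arm.
- A reader might infer that PGA-PA would show almost no difference between arms. That needs nearly all recurrences to receive bailout and r to be high. Section 2.1 keeps subjects who do not meet the bailout criteria on blinded drug, and the SAP gives no response rate after bailout.

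It is also fair that scoring bailout as failure is one valid strategy among others. The case for it here is consistency with PGIPS at the same visits.

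**Conclusion.** The concern holds as a defect of specification. At Weeks 8, 16 and 24 endpoint 17 either conflicts with itself or scores PGA-PA by a different rule from PGIPS, depending on which PGIPS endpoint is meant. On either reading the plan does not say explicitly whether the endpoint is split by bailout or tested.

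The choice of rule can matter a great deal. At Week 16 the gap between arms is about 46 points with bailout as failure, and anywhere from 46 down to 0 points under the observed denominator. These are illustrations from the design assumptions and from assumed values of b and r, not predictions.

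The consequence is bounded. Endpoint 17 is outside the gatekeeping and Hochberg family of Section 3.3, so the primary result, the major secondary endpoints and type I error control are unaffected. The text should be corrected, but the point does not threaten the trial's main conclusion.

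**What to change.** - For endpoint 17 at Weeks 8, 16 and 24, replace the observed-case denominator with the scoring of major secondary 3 and endpoints 5-6: ITT Week 8, 16 and 24 sets, with bailout on or before the visit, rescue at the assessment, or a missing assessment scored as not meeting the criterion.
- Keep the observed-case table for visits after Week 24 only.
- Extend the paragraph on endpoints 14-16 to 14-17, so that this later table is shown before and including bailout, without p-values.

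At minimum, make the 14-17 change and name the PGIPS endpoint that the cross-reference means.

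The cost is SAP wording and one re-programmed table. No new data are needed.
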